10.1 Correlative Studies

Bone marrow samples will be obtained on Day+100 and at 6, 12,18 and 24 months post transplant as part as our routine post transplant follow up. In addition, another BM aspirate sample, 3 cc, will be sent to HOTB.

Using a panel of aberrantly expressed cell surface proteins that are highly specific and sensitive for the detection of cells bearing these antigens, the samples will be assessed for residual MDS/AML cells. This analysis will be performed by multiparameter flow cytometry.

By using fluorescence activated cell sorting (FACS) and FISH technique, the samples will be assessed for residual involvement of the HSC compartment following transplantation.

Global methylation assay will also be assessed on the sorted cells by using anti- 5'-methylcytosine monoclonal antibody which will be provided by [name].

Peripheral blood sample will be obtained prior to start of Azacitidine treatment on C1D1 and at 12 and 18 months post transplant and will be stored at the Hematology-Oncology Tissue Bank (HOTB).

These samples will be sent to the clinical lab to assess azacitidine's effect on Tregs expression-
peripheral blood will be examined by flow using the markers CD3+CD4+CD25HICD127NEG.

11.1 TOXICITIES/SIDE EFFECTS

Toxicities will be graded according to NCI CTAE version 4.0 grades 3-4 only, except grades 1-4 hepatic toxicity (increased AST, ALT, alkaline phosphatase and bilirubin) and grades 1-4 GI toxicity (nausea, vomiting, diarrhea). The side effects and toxicities related to 5-azacitidine are listed below.

5'-azacitidine

Likely

- Nausea
- Vomiting
- Diarrhea
- Constipation
- Lowered white blood cell count that may lead to infection
- Lowered platelet count that may lead to an increase in bruising or bleeding
- Lowered red blood cells that may cause anemia, tiredness, or shortness of breath
- Chest pain
- Fever
- Fatigue and weakness
- Headache
- Dizziness
- Bruising
- Rash
- Dry skin
- Skin nodules
- Erythema
- Weight loss
- Abdominal pain
- Loss of appetite
- Joint pain
- Muscle Pain
- Breathlessness
- Upper respiratory tract infections as well as infections of the throat and sinuses
- Pneumonia

- Injection site bruising, pain or reaction
- Anxiety
- Insomnia

Less Likely:

- Abnormal heart beat
- Fainting spells
- Skin infections
- Upper abdominal pain
- Bleeding from the gums
- Difficulty eating
- Hemorrhoids
- Pain when urinating
- Urinary tract infection
- Muscle cramps
- Wheezing
- Fluid on the lungs
- Increased sweating
- Night sweats

Rare But Serious:

- Convulsions
- Anaphylaxis
- Bone marrow depression
- Congestive Heart Failure
- Stupor
- Coma

12.1 CRITERIA FOR THERAPEUTIC RESPONSE/OUTCOME ASSESSMENT

Definitions of events in the study period that are important for analysis and treatment

1. Disease relapse

Relapse of MDS or AML will be analyzed as to type and genetic origin of the leukemic cells. These will be defined by morphologic and/or cytogenetic criteria: an increasing number of blasts in the marrow over 5%, by presence of circulating blasts, or by presence of blasts in any extramedullary site as well as presence of previous cytogenetic abnormalities. Other

studies assessing for MRD, FACS and FISH assays will be evaluated but would not be considered disease relapse if positive since they are experimental..

2. Transplant related mortality

Includes fatal complications resulting from the therapy such as severe infection, hemorrhages and graft failure.

3. Immunologic reconstitution

Our previous studies have identified time points at which the various immunologic functions can be expected to return. Immunophenotyping and NK cell function will be performed on circulating lymphocytes of all patients.

T cell proliferation in response to PHA, candida, viral antigens and tetanus following immunization will be performed at approximately 6 months post transplant and every 3-6 months thereafter until normal values are reached.

4. Engraftment and chimerism

Engraftment will be documented by analysis of bone marrow cells as well peripheral blood cells for chimerism by standard karyotype or short tandem repeat analysis every 3 up to one year posttransplant.

13.0 CRITERIA FOR REMOVAL FROM STUDY

If at any time the patient is found to be ineligible for the protocol as designated in the section on Criteria for Patient/Subject Eligibility, the patient will be removed from the study. Intolerable toxicity would take a subject off protocol therapy, but not off study to continue to follow them since overall survival is a secondary objective. Also patients may be removed from the study if requested by the patient. Patients will need to receive a minimum of 4 cycles to be considered evaluable for protocol objectives. Patients who receive less than 4 cycles due to treatment-related toxicities will be considered evaluable for toxicity only and will not be replaced on study. Patients who relapse prior to receiving 4 cycles are considered evaluable per protocol. Patients who come off-study for reasons unrelated to toxicities before completing 4 cycles are considered inevaluable per protocol and will be replaced. Management will continue as per standard allogeneic HSCT guidelines.

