6.3 Subject Exclusion Criteria

Patients will be excluded from the trial if at time of enrollment:

1. Active uncontrolled bacterial, fungal or viral infection.
2. Evidence of uncontrolled graft-versus-host disease.
3. Pulmonary: new onset hypoxia
4. Known or suspected hypersensitivity to 5'-azacitidine or mannitol.
5. Evidence of residual disease either by increased blasts count (>5%) or persistence of previous known cytogenetics abnormalities.
6. Peripheral blood neutrophil chimerism: less than 95% donor.

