14.1 BIOSTATISTICS

This phase II trial will explore the efficacy of treating high-risk MDS and AML patients with 5'-azacitidine following TCD-HSCT. Based on historical MSKCC data for patients with advanced MDS and AML (adults and pediatrics) with high relapse risk, who meet the entry criteria, the two-year

cumulative incidence of relapse is 35%. Therefore, this intervention would be considered promising if the two-year relapse proportion is 15% or less. If the relapse proportion is 35% or greater, the 5-azacitidine intervention would not be considered promising. Therefore, using a single stage exact design, a total of 32 patients will accrue on study. At the end of the trial, if seven or fewer patients relapse by two years post treatment initiation, the trial will be considered promising. If, however, more than 8 patients relapse at any point the study will be considered unpromising and will be closed for further accrual. The type I and type II errors for this trial are 0.08 and 0.10, respectively. It is anticipated that enrollment will be completed in 5 years with an accrual of approximately 6-7 patients/year.

If a patient is found to be ineligible for reasons unrelated to disease relapse or progression, or is lost to follow-up, s/he will be replaced for the primary endpoint. If a patient dies for reasons unrelated to disease relapse or progression (i.e., treatment related mortality), s/he will remain as part of the 32 patient cohort. Treatment-related mortality will be monitored as part of the stopping rules discussed below.

In order to reduce patient risk and confirm the safety of 5'-azacitidine in this setting, the study design includes early termination in event of severe neutropenia, severe thrombocytopenia, and treatment-related mortality. The boundaries are based on accrual of 32 patients. The calculations in the table below are based on marginal probabilities.

Failure Type	# of failures needed to stop the study	Failure rate in the population	Probability boundary is crossed
Neutropenia (Grade III-IV)	3 in the first 8 patients 4 in the first 14 patients 5 in the first 20 patients 6 in the first 27 patients 7 at any point	0.1	0.1
		0.3	0.92
Thrombocytopenia (Grade III-IV)	3 in the first 8 patients 4 in the first 14 patients 5 in the first 20 patients 6 in the first 27 patients 7 at any point	0.1	0.1
		0.3	0.92
	3 in the first 5 patients 4 in the first 8 patients 5 in the first 12 patients	0.15	0.07

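### Ineligibility has no time limit in sections 13 and 14.1, so a treated patient can be excluded and replaced for the primary endpoint after a relapse is known

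*Combined protocol and SAP*

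**What the plan says.** Section 13.0 opens with the removal rule: "If at any time the patient is found to be ineligible for the protocol", as judged against the eligibility section, then "the patient will be removed from the study". No cut-off is given, either at first dose or before the outcome is known.

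Section 14.1 adds the replacement rule for the primary endpoint: "If a patient is found to be ineligible for reasons unrelated to disease relapse or progression, or is lost to follow-up, s/he will be replaced".

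Section 13.0 treats patients who stop for toxicity differently. They leave protocol therapy "but not off study to continue to follow them since overall survival is a secondary objective". There is no matching provision for patients found ineligible.

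Section 13.0 also says: "Patients who relapse prior to receiving 4 cycles are considered evaluable per protocol". That sentence deals with the four-cycle minimum and is silent on eligibility.

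Section 14.1 sets 32 patients, a two-year relapse rate of 35% as unpromising and 15% as promising, a promising result at seven or fewer relapses, and closure to accrual once more than eight have occurred. The stated type I and type II errors are 0.08 and 0.10. Section 2.1 measures overall survival from the start of azacitidine.

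**The concern.** The section 14.1 qualifier concerns why the patient was ineligible. It does not concern when this was discovered or what had happened to the patient by then. A patient who relapses, and whose entry creatinine or ejection fraction is then found to have missed the criterion, is ineligible for a reason unrelated to relapse. Read together, the two sections remove and replace that patient. For some criteria the reason is itself open to argument: whether a breach of the exclusion "Peripheral blood neutrophil chimerism: less than 95% donor" (section 6.3) is unrelated to relapse would be judged by staff who know that the patient relapsed.

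A relapse is a natural prompt to look back at the entry work-up, so deviations may be found more often in relapsers. If so, relapses drop out of the count and are replaced by fresh patients, most of whom will not relapse. Nothing requires the eligibility finding to be made without knowledge of outcome, and no analysis of all treated patients is planned.

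The second stake is follow-up. Survival runs from first azacitidine, so every dosed patient belongs in that analysis. Removal from the study, set against the explicit retention of toxicity stoppers, implies that a dosed patient later found ineligible leaves relapse and survival follow-up. Sections 13 and 14.1 also do not say whether such a patient still counts toward the neutropenia, thrombocytopenia and treatment-related mortality boundaries.

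**Working it through.** **Inputs from section 14.1:** n = 32; promising if X ≤ 7 relapses; null rate p = 0.35; target rate 0.15. **Assumed, because the documents give no figure:** f, the share of relapsers excluded and replaced because an entry deviation is found after the relapse, at 3%, 5% and 10%.

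**1. The plan's own figures (exact binomial).**
- Type I error: P(X ≤ 7 | 32, 0.35) = 0.0818, which is the stated 0.08.
- Type II error: 1 − P(X ≤ 7 | 32, 0.15) = 1 − 0.9042 = 0.0958, which is the stated 0.10.

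**2. Scale of the assumption.** Expected relapses under the null are 32 × 0.35 = 11.2. Rates of 3%, 5% and 10% therefore mean 0.34, 0.56 and 1.12 replaced relapsers on average.

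**3. Late findings independent of outcome.** Replacement leaves the relapse rate at 0.35, so type I error remains 0.0818.

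**4. Upper figure: relapsers replaced throughout the trial.** The effective rate among the 32 counted is p(1 − f)/(1 − fp). For f = 0.05 this is 0.35 × 0.95/(1 − 0.0175) = 0.3325/0.9825 = 0.338. Type I error is then P(X ≤ 7) at that rate. This requires each exclusion to occur before the count passes 8, since the closure rule would otherwise apply.

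**5. Lower figure: rescue only at a count of exactly 8.** P(X = 8 | 32, 0.35) = 0.0766. The chance that at least one of the eight relapsers has a late-found deviation is 1 − (1 − f)^8, and one replacement stays relapse-free with probability 0.65. Type I error is 0.0818 + 0.0766 × 0.65 × [1 − (1 − f)^8].

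| f (assumed) | Effective null rate | Type I error, step 4 | 1 − (1 − f)^8 | Type I error, step 5 |
|---|---|---|---|---|
| 3% | 0.343 | 0.095 | 0.216 | 0.093 |
| 5% | 0.338 | 0.104 | 0.337 | 0.099 |
| 10% | 0.326 | 0.132 | 0.570 | 0.110 |

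**6. Extreme case.** If every trial with exactly eight relapses contained one replaceable relapser, type I error would be 0.0818 + 0.0766 × 0.65 = 0.132.

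**The case against.** The strongest reply is that late, outcome-driven discovery should be rare. Section 15.2 requires a signed eligibility checklist at registration, section 8.1 a pretreatment evaluation, and section 16.2 weekly registration reports and random-sample compliance audits at least twice a year. Most criteria are recorded baseline values. These checks do not depend on outcome and make late findings less likely, which is why the rates above can only be assumed. They do not bar late findings, and section 13 expressly provides for them.

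It can also be said that excluding ineligible patients is defensible, because the 35% benchmark describes historical patients who satisfied the entry criteria. That stands as a reason for a sensitivity analysis without them. It does not justify exclusions decided after the outcome is known.

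Three stronger readings are tempting, and the documents do not support them:
- **That every patient found ineligible is replaced.** Section 14.1 limits replacement to reasons unrelated to relapse or progression. Patients who relapse before four cycles remain evaluable (section 13), and non-relapse deaths stay in the 32 (section 14.1).
- **That safety data are lost.** Section 17.3 continues serious adverse event reporting for 30 days after the last treatment, and later for possibly related events, and provides safety follow-up for all patients. The gap is in relapse and survival follow-up. Even that is inferred from the removal wording and the contrast with toxicity stoppers, and is not stated outright.
- **That type I error is 0.132.** That figure needs either the 10% rate with every exclusion made before the count passes 8, or a replaceable relapser in every trial that reaches exactly eight.

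**Conclusion.** The concern holds in limited form. As written, a dosed patient who has already relapsed can be removed and replaced for an entry deviation found afterwards, and no outcome-blind rule or all-treated analysis guards against it. The bias is possible, not certain. Type I error stays at 0.082 if discovery is independent of outcome. It rises to about 0.093 to 0.095, 0.099 to 0.104, or 0.110 to 0.132 if 3%, 5% or 10% of relapsers are replaced because review follows relapse. Those rates are assumptions, and each range runs from rescue only at a count of eight to replacement throughout the trial. Separately, the plan does not secure relapse and survival follow-up for dosed patients later found ineligible. Because one event decides the result and the remedy is cheap, this should be corrected.

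**What to change.** In sections 13 and 14.1, allow replacement for ineligibility only when it is found before the first azacitidine dose. State that a dosed patient later found ineligible is neither removed nor replaced on that ground, and remains in relapse and survival follow-up and in the safety boundary counts. Report all late-found entry deviations, with one sensitivity analysis that excludes those patients, to preserve the comparison with the 35% benchmark.

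The sample size, the seven-or-fewer rule and the stated errors (0.0818 and 0.0958) are unchanged. The cost is a few sentences in two sections. Marrow assessments are already scheduled to 24 months post transplant, so most of the follow-up is in place. The downside is slight dilution by a few ineligible patients. The four-cycle evaluability rule and withdrawal at the patient's request are separate matters, and this change leaves both as they are.

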2.1 OBJECTIVES AND SCIENTIFIC AIMS

The aim of this prospective phase II trial is to evaluate the efficacy and confirm the safety of 5'-azacitidine after allogeneic T cell depleted (TCD) hematopoietic stem cell transplant (HSCT) from histocompatible matched or mismatched related or unrelated donor in patients with Myelodysplastic syndrome (MDS) and Acute Myelogenous Leukemia (AML) who are at high risk for relapse.

Primary objective:

To evaluate whether maintenance treatment post transplant with 5-azacitidine can reduce the relapse rate over the current standard of care for high-risk MDS and AML patients.

Secondary objectives:

1. To assess overall survival from the time of 5-azacitidine initiation.
2. To confirm the safety and tolerability of low dose 5'-azacitidine by measuring the frequency of transfusions, frequency of bleeding, frequency of serious infections, and use of G-CSF support.
3. To evaluate graft function and myeloid and T cell chimerism after administration of low dose 5'-azacitidine
4. To evaluate the incidence of acute and chronic GvHD following the initiation of 5-azacitidine.

Correlative Objectives:

Correlate treatment with low dose 5'-Azacitidine with:

1. Gene specific methylation in the hematopoietic stem cell (HSC) compartment in CD 34 cells subpopulations.
2. Recurrence of cytogenetic abnormalities in the hematopoietic stem cell (HSC) compartment in CD34 cells subpopulations.
3. Normalization of myeloid progenitor frequencies known to be altered in MDS.
4. Level of regulatory T cells (CD4+CD25-FoxP30).

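### The 4-cycle evaluability rule, if applied to overall survival and GvHD counted from first dose, biases survival upward and GvHD in an unknown direction, and it conflicts with other text in the protocol

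*Combined protocol and SAP*

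**What the plan says.** Section 13.0 (Criteria for removal from study) sets the entry condition: "Patients will need to receive a minimum of 4 cycles to be considered evaluable for protocol objectives". It then sorts patients with fewer than 4 cycles into three groups:

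- Early relapse: "Patients who relapse prior to receiving 4 cycles are considered evaluable per protocol".
- Toxicity: "Patients who receive less than 4 cycles due to treatment-related toxicities will be considered evaluable for toxicity only and will not be replaced on study".
- Other reasons: "Patients who come off-study for reasons unrelated to toxicities before completing 4 cycles are considered inevaluable per protocol and will be replaced". Section 4.3 (Intervention) repeats this replacement rule.

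The same section also says: "Intolerable toxicity would take a subject off protocol therapy, but not off study to continue to follow them since overall survival is a secondary objective".

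Section 2.1 lists as secondary objectives "To assess overall survival from the time of 5-azacitidine initiation" and "To evaluate the incidence of acute and chronic GvHD following the initiation of 5-azacitidine". Both clocks therefore start at first dose.

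Section 14.1 (Biostatistics) assigns Kaplan-Meier to survival and a cumulative incidence function to GvHD, and states no analysis set for either. On the cohort of 32, it replaces patients who prove ineligible or are lost to follow-up, for the primary endpoint. It keeps in that cohort a patient who dies of a cause other than relapse or progression.

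**The concern.** Entry to the evaluable set depends on a later event (receiving cycle 4), while time is counted from the first dose. A patient who neither relapses nor reaches cycle 4 is either evaluable for toxicity alone or replaced. If that set is used for survival, a relapse-free death in the first cycles cannot appear on the curve, so the relapse-free members of the set carry guaranteed survival time. The condition is written for protocol objectives in general, and the secondary objectives are protocol objectives.

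At stake is how survival and GvHD are read in a single-arm trial that has no concurrent group to expose the inflation. The conflicting passages also leave the choice of analysis set open until outcomes are known.

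**Working it through.** **1. The plan's own figures.** Section 14.1 gives error rates of 0.08 and 0.10 for 32 patients, with 7 or fewer relapses counted as promising (35% against 15%). Exact binomial: P(X ≤ 7 | 32, 0.35) = 0.0818, and 1 − P(X ≤ 7 | 32, 0.15) = 0.0958. The stopping boundaries, computed patient by patient, are crossed with probability 0.098 and 0.924 for the haematologic rules (stated 0.1 and 0.92) and 0.074 and 0.931 for treatment-related mortality (stated 0.07 and 0.93). All reproduce, and none uses the survival or GvHD set. The plan states no figure for survival or GvHD.

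**2. Length of the guaranteed period.** Cycles are 28 days (section 9.1). Cycle 4 starts nominally 3 × 28 = 84 days after first dose, and four full cycles end at 4 × 28 = 112 days. Adding one 60-day hold, the longest in the section 9.1 table, gives 144 and 172 days.

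**3. Effect on survival if section 13.0 governs.** Let S be true 2-year survival and e the share of treated patients who die relapse-free before cycle 4 and are dropped. Then reported survival = S / (1 − e). The values of e and S are assumptions; the documents give neither.

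| Assumed e | Patients of 32 | True 60% reads | True 50% reads |
|---|---|---|---|
| 3% | 1.0 | 0.60/0.97 = 61.9% | 51.5% |
| 6% | 1.9 | 0.60/0.94 = 63.8% | 53.2% |
| 10% | 3.2 | 0.60/0.90 = 66.7% | 55.6% |

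The formula drops only early deaths. If living early stoppers are dropped too, the result also depends on their later survival.

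**4. A second way to choose e.** The mortality boundary in section 14.1 uses rates of 15% and 40%. Read as 2-year rates with constant hazard (again an assumption), e = 1 − exp(−h × d), with h = −ln(1 − rate)/730:

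- 15%: e = 1.9% by day 84 and 2.5% by day 112.
- 40%: e = 5.7% by day 84 and 7.5% by day 112.

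A true 60% would then read between 61.1% and 64.9%.

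**5. Effect on GvHD.** Take an illustrative 5 cases in 32 (15.6%) and drop 3 early relapse-free deaths, leaving 29. If none of the three had GvHD, the result is 5/29 = 17.2%. If one, two or three had it, the result is 4/29 = 13.8%, 3/29 = 10.3% or 2/29 = 6.9%. Dropping competing deaths raises the incidence and dropping early cases lowers it, so the sign is not fixed.

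**6. The passages side by side.** For a relapse-free patient with fewer than 4 cycles:

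- Stops for toxicity and lives: followed for survival, yet "will be considered evaluable for toxicity only and will not be replaced on study" (both in section 13.0).
- Dies without relapse: outside the evaluable set under section 13.0, but inside the cohort of 32 under section 14.1.
- Comes off study for another reason: replaced (sections 4.3 and 13.0), with no survival follow-up stated.

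Applying both sections together keeps the early stopper who dies and drops the one who lives. Inclusion would then depend on outcome, which tends to lower survival instead.

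**The case against.** The strongest reply is that section 14.1 keeps relapse-free deaths in the cohort of 32. Its replacement sentence is limited to the primary endpoint, but its sentence on deaths carries no such limit. On that reading the inflation in step 3 is zero. Section 13.0 also follows patients who stop for toxicity expressly for survival, so its restriction to toxicity could be meant for efficacy only. This stands in part: exclusion of early deaths is one reading of conflicting text. It does not remove the problem, because section 14.1 never says that the cohort of 32 is the survival or GvHD set, and it says nothing of early stoppers who live.

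Other points on this side also stand:

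- Treatment-related mortality has its own boundaries with no stated 4-cycle condition. A reader might infer that early drug-related deaths are hidden from safety monitoring; the documents do not support that.
- A reader might infer that anyone who stops for GvHD or infection leaves the study and has no survival recorded. Section 13.0 separates leaving therapy from leaving the study and does not say this. The follow-up of such patients is simply not stated.
- The only historical benchmark is for relapse. No success criterion rests on survival or GvHD.
- The size is assumed. The 10% upper end exceeds what step 4 gives even for the 40% rate, and the standard error of a 60% survival in 32 patients is √(0.6 × 0.4/32) = 8.7 points.

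**Conclusion.** The concern holds conditionally. Section 13.0 is the only text that says who is evaluable for protocol objectives. If it is followed as written, relapse-free patients in the survival set cannot die before cycle 4, nominally day 84, and survival is biased upward. Under assumed early relapse-free death rates of 3% to 10%, a true 60% reads 61.9% to 66.7%, an inflation of 1.9 to 6.7 points. If section 14.1 governs and its cohort is the survival set, this bias is zero. GvHD incidence would be biased in an unknown direction.

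Two stronger readings are tempting and not supported. One is that the rule certainly removes every relapse-free early death; section 14.1 says otherwise for its cohort. The other is that the whole survival set has guaranteed time; patients who relapse before cycle 4 stay evaluable and their early deaths count.

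The contradiction does not depend on the assumed rates. The primary design's error rates and the treatment-related mortality boundaries are not affected.

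**What to change.** Before any analysis, reconcile sections 4.3, 13.0 and 14.1 so that they give one account of relapse-free deaths, toxicity stoppers and other early stoppers. Specifically:

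1. In section 13.0, limit the 4-cycle condition so that it does not apply to overall survival, GvHD, graft function or chimerism, and remove the restriction to toxicity for these endpoints.
2. In section 14.1, name the analysis set for them: all patients who received at least one dose, counted from first dose, whatever the number of cycles or the reason for stopping.
3. State that death is a competing event in the acute and chronic GvHD cumulative incidence, and whether relapse is one too.
4. In sections 4.3 and 13.0, separate stopping treatment from leaving the study, and continue follow-up of every dosed patient for relapse, GvHD and survival unless consent is withdrawn. Replacing a patient for the primary endpoint should not end that follow-up.

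This removes the bias under either reading. The cost is protocol wording and continued follow-up of a few early stoppers, largely within the routine post-transplant marrow and chimerism visits already scheduled to 24 months. Reported survival may be slightly less favourable.

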9.1 TREATMENT/INTERVENTION PLAN

1. 5'-azacitidine will be given at a dose of 32mg/m² for 5 consecutive days subcutaneously. Treatment will be given every 28 days (cycle). Treatment will be given up to a year post transplant.
2. CBC will be checked weekly during the first 2 cycles, and if stable every 2 weeks with following cycles. CBC results from tests performed externally will be accepted for Days 8, 15, and 22 of C1 and C2 and Day 15 of subsequent cycles. Comprehensive metabolic panel will be checked at the beginning of every cycle.
3. Pregnancy test will be checked for women at child bearing age prior to start of each cycle.
4. Bone marrow studies (day 100, and 6, 12, 18 and 24 months post transplant) for assessment of disease status and chimerism. Peripheral blood chimerism status at day 100, and 6, 12, 18 and 24 months post transplant will be tested as part of routine post transplant evaluation
5. Peripheral blood lymphocytes phenotyping and in-vitro response to standard panel of mitogen will be assessed as part of routine post transplant assessment
6. Bone marrow samples for correlative studies will be tested at the same time that patients are undergoing routine BM studies. These tests are considered experimental.
7. Peripheral blood samples for correlative studies will be collected prior to start of Azacitidine treatment on C1D1 and at 12 and 18 months post transplant. These tests are considered experimental.

Dose modifications

Event	Modification
ANC <1000/uL for > 4 days.	Drug held until resolved (ANC 1500) and up to 60 days. If after 60 days there is no neutrophils recovery the treatment will be permanently discontinued.
• If by next cycle ANC is 1000-1500, not G-CSF dependent	Resume therapy with 50% dose reduction
• If by next cycle ANC fully recovered, >1500 not G-CSF dependent	Resume full therapy dose
Platelets <10,000/uL for > 4 days, or if transfusion dependent to keep count>10,000/ uL	Drug held until resolved (>50,000) and up to 60 days.

• If by next cycle Platelets are 10,000-50,000, not transfusion dependent	Resume therapy but with 50% dose reduction
• If by next cycle Platelets >50,000	Resume full therapy dose
Hemoglobin < 8g/dL for > 4 days or if transfusion dependent	Drug held until resolved (> 8g/dL) and up to 60 days.
• If by next cycle hemoglobin >8g/dL	Resume full therapy dose
Hepatic toxicity – Drug related grade 3-4	Drug stopped

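### Patients stopped early for toxicity are neither counted for relapse nor replaced, yet the limit of 7 relapses assumes all 32; one such stop takes type I error from 0.082 to 0.101.

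*Combined protocol and SAP*

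**What the plan says.** Section 14.1 (Biostatistics) fixes the design: "using a single stage exact design, a total of 32 patients will accrue on study". The decision rule follows: "if seven or fewer patients relapse by two years post treatment initiation, the trial will be considered promising". The null and target relapse proportions are 35% and 15%, and the stated type I and type II errors are 0.08 and 0.10. The section then covers some patients who do not complete. One who is ineligible for reasons other than relapse or progression "or is lost to follow-up, s/he will be replaced for the primary endpoint". One who dies without relapse or progression, including from treatment, is kept: "s/he will remain as part of the 32 patient cohort". Patients who stop early for toxicity are not mentioned.

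Section 13.0 (Criteria for Removal from Study) deals with them:

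- The general rule is "Patients will need to receive a minimum of 4 cycles to be considered evaluable for protocol objectives".
- Patients with fewer than 4 cycles "due to treatment-related toxicities will be considered evaluable for toxicity only and will not be replaced on study".
- The next sentence is "Patients who relapse prior to receiving 4 cycles are considered evaluable per protocol".
- Patients who leave before 4 cycles for reasons other than toxicity are inevaluable and are replaced.

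The same section keeps patients with intolerable toxicity on study, but the reason it gives is overall survival, not relapse.

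**The concern.** The two sections do not agree on who belongs to the 32. Two readings are open.

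- **Reading (a), the literal one.** A patient stopped for toxicity before 4 cycles is outside the efficacy analysis and nobody takes the place. Fewer than 32 patients can then contribute a relapse, and the limit is still 7.
- **Reading (b).** The sentence on relapse before 4 cycles also covers a relapse that follows an early toxicity stop. All 32 patients are then judged.

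The limit is a fixed count, so leaving patients out can only lower the number of relapses set against it. The error therefore runs one way, towards declaring an ineffective treatment promising. The trial has a single arm and its conclusion rests on this one count, so nothing else in the analysis would correct it. With the rule unsettled, the choice of reading could also be made after the relapses are known.

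A smaller conflict concerns a treatment-related death before cycle 4. Section 14.1 keeps that patient in the 32, while Section 13.0 makes the patient evaluable for toxicity only.

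**Working it through.** **Inputs from Section 14.1.** n = 32; limit 7; null relapse proportion 0.35; target 0.15; stated errors 0.08 and 0.10.

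**Assumed input.** k, the number of patients stopped for toxicity before 4 cycles. The documents forecast no figure, so a range is shown.

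**Step 1: reproduce the plan.** With X binomial:

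- Type I error = P(X ≤ 7 | 32, 0.35) = 0.0818.
- Type II error = P(X ≥ 8 | 32, 0.15) = 1 − 0.9042 = 0.0958.

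Both agree with the stated 0.08 and 0.10. Neighbouring limits do not: a limit of 6 gives 0.036 and 0.195, and a limit of 8 gives 0.158 and 0.041. The stated errors therefore rest on 32 patients who all count.

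**Step 2: reading (a).** Type I error = P(X ≤ 7 | 32 − k, 0.35). It makes no difference whether the k patients leave the denominator or stay in it as non-relapses, because only the count is compared with 7.

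| k | Patients counted | Type I error | P(X ≤ 7) at 0.15 |
|---|---|---|---|
| 0 | 32 | 0.082 | 0.904 |
| 1 | 31 | 0.101 | 0.918 |
| 2 | 30 | 0.124 | 0.930 |
| 3 | 29 | 0.151 | 0.941 |
| 4 | 28 | 0.182 | 0.951 |

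**Step 3: partial counting.** Suppose half of the stoppers' relapses are counted, for instance because the rule is applied unevenly. The count is then Bin(32 − k, 0.35) + Bin(k, 0.175), and P(X ≤ 7) is 0.102 for k = 2 and 0.126 for k = 4.

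**Step 4: a different relapse risk in stoppers.** Step 2 gives stoppers the same 35% risk as everyone else. Now hold the whole-cohort average at 35% and give stoppers a risk s. The remaining patients have risk (32 × 0.35 − k·s)/(32 − k). For s = 0.15 and k = 1 this is (11.2 − 0.15)/31 = 0.356.

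| Stoppers' risk s | k = 1 | k = 2 | k = 4 |
|---|---|---|---|
| 0.15 | 0.089 | 0.096 | 0.112 |
| 0.35 | 0.101 | 0.124 | 0.182 |
| 0.50 | 0.111 | 0.148 | 0.251 |

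The size moves with s, but every entry exceeds 0.082.

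**Step 5: toxic deaths.** A patient who dies without relapse adds nothing to the count, so the decision is the same either way. Only the reported proportion changes: with one such death and 7 relapses, 7/32 = 21.9% against 7/31 = 22.6%.

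**The case against.** The best case against is that the text gives real support to reading (b). A patient stopped at cycle 2 who later relapses has, literally, relapsed without ever receiving 4 cycles, and the sentence on such relapses comes straight after the toxicity-only sentence with no exception. These patients remain on study. The marrow schedule in Section 9.1 is set by time since transplant, not by treatment status. Non-replacement is compatible with keeping them in the 32. On this reading type I error is 0.082 and nothing is wrong with the numbers. That stands as far as it goes: inflation is not certain. But the restriction to toxicity is explicit wording for the opposite reading, and no sentence chooses between them.

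Second, early stops may be few. Section 3.4 describes the dose as tolerable after transplant, and most haematologic toxicity in the Section 9.1 table leads to holding or reducing the drug. This also stands, so the figures for three or four stops should not set the weight of the point. Even so, Section 9.1 provides for permanent discontinuation, Section 13.0 has a rule for exactly this group, and one stop is enough to pass 0.08. With no early toxicity stop at all, 0.08 holds on either reading.

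Third, stoppers may not share the 35% risk. That changes the size, as Step 4 shows, but not the direction.

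Fourth, the partial-counting case in Step 3 matches neither reading. It is best taken as an illustration of an inconsistently applied rule.

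Last, the conflict over toxic deaths does not alter the decision. That is conceded.

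**Conclusion.** The concern holds and should be fixed. Sections 13.0 and 14.1 leave open whether relapses after an early toxicity stop count, and the most literal reading makes the stated type I error of 0.08 untrue from the first such stop. On that reading, with stoppers at the same 35% risk, it is 0.101 for one stop and 0.182 for four. If stoppers' own risk is only 15%, it is 0.089 for one and 0.112 for four. The number of stops is assumed throughout. Confidence is high that the conflict exists and which way it pushes the error. The size depends on how many patients stop early and on their relapse risk.

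**What to change.** **Preferred.** State in Section 13.0, and mirror in Section 14.1, that patients stopped before 4 cycles for treatment-related toxicity, including those who die of it, stay in the 32-patient cohort for the primary endpoint. Record their relapse status to two years from treatment start. Leave the replacement rule for withdrawals unrelated to toxicity as it is.

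The existing visits can carry most of this: "Bone marrow studies (day 100, and 6, 12, 18 and 24 months post transplant) for assessment of disease status and chimerism". They stop short of the endpoint, though. Treatment starts 60 to 120 days after transplant, so two years from treatment start falls about 26 to 28 months after transplant (24 plus roughly 2 to 4). A later status check is needed, as it is for every patient.

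**Cost.** Wording only, with no added patients. Type I error is 0.082, and power is 0.904 if the relapse proportion across the whole cohort is 15%. Power is lower if stoppers gain no benefit. With k stoppers at 35% and the rest at 15%, the count is Bin(32 − k, 0.15) + Bin(k, 0.35), and power is 0.886, 0.866 and 0.819 for k = 1, 2 and 4. Put as a share q of patients stopping, the overall proportion is 0.15(1 − q) + 0.35q: 0.16 at q = 5% (power 0.872) and 0.17 at q = 10% (power 0.835). This loss comes from patients who gain no benefit, which the planned 32-patient analysis is meant to reflect.

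**Alternative.** If the exclusion is kept, Section 14.1 must give the limit for each evaluable n and restate power:

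| Evaluable n | Limit | Type I error | Power at 0.15 |
|---|---|---|---|
| 31 | 6 | 0.046 | 0.827 |
| 30 | 6 | 0.059 | 0.847 |
| 29 | 6 | 0.074 | 0.867 |
| 28 | 5 | 0.039 | 0.765 |
| 27 | 5 | 0.051 | 0.790 |
| 26 | 5 | 0.065 | 0.815 |

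At n = 25 a limit of 5 gives 0.083, slightly above the planned design's 0.082. This route costs more power than the first when stops are few, and it still drops treated patients from the primary endpoint.
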